#### **Percentages of Subjects With Reduction in Migraine Days per Month in the OLE Phase**

Analyses will be based on evaluable OL rimegepant mITT subjects with eDiary efficacy dates in the OP and on-OL rimegepant efficacy analysis periods.

The number and percentage of evaluable OL rimegepant mITT subjects with reductions from the OP in the number of migraine days per month in the OLE phase will be presented by treatment group and overall, and severity (total; moderate or severe) in each month of the OLE phase and overall OL mean (see Section 6.3.1.2 for months). Reduction from OP categories will be same as those defined previously for the DBT phase. Analyses by month will be presented using the analogous Non-Evaluable = Failure and Non-Evaluable = Missing methods described previously for the DBT phase. Analyses for the Non-Evaluable = Failure method will only be shown in the Addendum Report. Results will support the exploratory objective about OLE phase efficacy.

### 6.3.2.2 *Rescue Medication Days per Month*

During the DBT and OLE phases, subjects may record taking triptan, ergotamine, and other medications to treat headache or during aura in the eDiary evening report headache log or follow-up headache log.

Rescue medication days per month will be assessed as “rescue medication days per 4 weeks” to correspond with the 4-week visit schedule. Rescue medication days per month are based on data from the previous visit to the current visit (i.e., 4-week interval) where a rescue medication day is defined as a day of efficacy data with complete reference time point date and a “yes” response to at least one of the following questions: taking triptan to treat headache or during aura; taking ergotamine to treat headache or during aura; taking other medication to treat headache.

#### **Rescue Medication Days per Month in the DBT Phase**

Analyses are based on evaluable mITT subjects with eDiary reference time point dates in the on-DBT efficacy analysis period.

The number of rescue medication days per month in the DBT phase will be prorated to 28 days and derived as follows:

- Month (i.e., 4-week interval) in the on-DBT efficacy analysis period:  $28 \times (\text{total number of rescue medication days in the month}) / (\text{total number of efficacy data days in the month})$ .  
Subjects must have  $\geq 14$  days of efficacy data (not necessarily consecutive) in the specified month to be evaluable.
- Overall DBT mean:  $28 \times (\text{total number of rescue medication days through Month 3 in the on-DBT efficacy analysis period}) / (\text{total number of efficacy data days through Month 3 in the on-DBT efficacy analysis period})$ .

#### **Descriptive Analyses**

The number of rescue medication days per month in the DBT analysis period will be summarized descriptively as a continuous parameter (including 2-sided normal 95% CIs for mean) by treatment group in each month of the DBT phase and overall DBT mean.

#### **Treatment Group Comparisons**

A generalized linear mixed effect model will have the following variables: number of rescue medication days per month as the dependent variable; subject as a random effect; treatment group, prophylactic migraine medication use at randomization, month (i.e., months 1 to 3 of the DBT phase), and the month-by-treatment group interaction as fixed effects. The model will be repeated by prophylactic migraine medication use at randomization (yes, no). The following model estimates will be reported:

- LSM, SE, and 95% CI by month and randomization stratum (yes, no, overall) for each treatment group
- Difference in LSMs between treatment groups (rimegepant – placebo), SE, 95% CI, and p-value by randomization stratum (yes, no) for each month
- Difference in LSMs between treatment groups (rimegepant – placebo), SE, 95% CI, and p-value for each month. Results in the last month will support the third secondary objective, whereas results in the other months will support an exploratory objective.
- Overall LSM, SE, and 95% CI by randomization stratum (yes, no, overall) for each treatment group
- Difference in overall LSMs between treatment groups (rimegepant – placebo), SE, 95% CI, and p-value by randomization stratum (yes, no)
- Difference in overall LSMs between treatment groups (rimegepant – placebo), SE, 95% CI, and p-value. Results will support an exploratory objective.

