6.3 Efficacy Assessments

The eDiary will be used daily to record rescue medication dosing occurrences (i.e., with triptans, ergotamine, or other), and migraine occurrence, characteristics, and severity during the observation period, double-blind treatment phase, and open-label extension phase.

Efficacy assessments will be derived from eDiary data, and will include the number of migraine days by severity (total; moderate or severe) per month, number of rescue medication days per month, and MRM days per month, in each month by study period.

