9.5 Secondary Endpoint(s)

The number of subjects that experience at least a 50% reduction in the mean number of moderate or severe migraine days per month in the last 4 weeks of the double-blind treatment phase will be analyzed using a stratified Cochran-Mantel-Haenszel (CMH) test after the missing data are imputed as non-response.

The change from baseline in the mean number of migraine days per month over the entire double-blind treatment phase (Weeks 1 to 12) will be assessed with the same statistical model used to analyze the primary endpoint.

The use of rescue medications (mean number of days per month) in the last 4 weeks of the double-blind treatment phase will be assessed using a generalized linear mixed effects model that is similar in structure to that used for the primary analysis. Rescue medications are defined in Section 5.5.

The change from baseline in the mean number of migraine days per month in the first 4 weeks (Weeks 1 to 4) of the double-blind treatment phase will be assessed with the same statistical model used for to analyze the primary endpoint.

The investigators will determine the severity of adverse events (AEs) and the relationship of AEs to study therapy. The investigators' terms will be coded and grouped by system organ class using the latest version of the Medical Dictionary for Regulatory Activities (MedDRA) available to the analyst. AEs will be presented by system organ class and preferred term. If a subject had an adverse event with different severities over time, then only the worst severity will be reported. Tabulations will be made for the frequency of unique subjects with adverse events (by severity, by relationship to study drug, and overall), serious adverse events, adverse events leading to treatment discontinuation, hepatic-related adverse events (by severity, by relationship to study drug, and overall), and hepatic-related adverse events leading to treatment discontinuation from case report forms.

The frequency of unique subjects with clinically significant laboratory test abnormalities will be tabulated based on Grade 3 - 4 clinical laboratory evaluations graded using the latest version of Common Terminology Criteria for Adverse Events (CTCAE).

Other safety analyses will be described in the statistical analysis plan.

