### **6.3.1 Reduction in Migraine Days per Month**

Subjects are instructed to report headache status (yes, no), severity (mild, moderate, severe, none), and characteristics (e.g., aura, nausea, vomiting), as well as medication taken to treat headache or during aura, in the eDiary evening report headache log or follow-up headache log recorded every day in the OP, DBT, and OLE phases.

Migraine days per month will be assessed as “migraine days per 4 weeks” to correspond with the 4-week visit schedule. Migraine days per month are based on data from the previous visit to the current visit (i.e., 4-week interval), and are prorated to account for missing migraine reports.

A by-subject listing will present efficacy analysis period and the following from the eDiary evening report headache log and follow-up headache log for enrolled subjects who had a “yes” response to having a headache or an aura-only event: headache status; aura-only event status, headache lasting  $\geq 30$  minutes status; headache start and end dates; headache severity; headache pain features present\* (i.e., unilateral, pulsating, worsen or avoid activity), headache pain characteristics present (i.e., aura, nausea, vomiting, photophobia, phonophobia); medication used to treat headache or during aura\* (i.e., study medication, additional study medication, triptan, ergotamine, other medication). Migraine days, rescue medication days, and MRM days will also be identified in the listing. Parameters marked with “\*” will be displayed only for subjects with a “yes” response to these questions. COVID-19 visit impact code for visits impacted by COVID-19 will be displayed (see Section 9.1.5.2).

Another by-subject listing for treated subjects will present the following: number of migraine days per month by severity (total; moderate or severe) in the OP efficacy analysis period, overall DBT mean, overall OL rimegepant mean, and in each month (i.e., 4-week interval) in the on-DBT and on-OL rimegepant efficacy analysis periods; number of days of efficacy data in the aforementioned intervals, overall DBT mean, and overall OL rimegepant mean; and migraine day values, changes and percent changes from OP in the aforementioned intervals, overall DBT mean, and overall OL rimegepant mean.

See Section 7.6.2.2 for the definitions of efficacy data days and migraine days.

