#### Principal Analysis

The principal analysis of the primary endpoint will use a generalized linear mixed effect model with the following variables: change from the OP in number of total migraine days per month as the dependent variable; subject as a random effect; number of total migraine days per month in the OP as a covariate; treatment group, prophylactic migraine medication use at randomization, month (i.e., months 1 to 3 of the DBT phase), and the month-by-treatment group interaction as fixed effects. The model will be repeated by prophylactic migraine medication use at randomization (yes, no). The following model estimates will be reported:

- Least-squares mean (LSM) change from OP, SE, and 95% CI by month and randomization stratum (yes, no, overall) for each treatment group
  - Difference in LSM changes from OP between treatment groups (rimegepant – placebo), SE, 95% CI, and p-value by randomization stratum (yes, no) for each month
-

- Difference in LSM changes from OP between treatment groups (rimegepant – placebo), SE, 95% CI, and p-value for each month. Results in the last month will support the primary objective, results in the first month will support the fourth secondary objective, and results in the second month will support the first exploratory objective.
- Overall LSM change from OP, SE, and 95% CI by randomization stratum (yes, no, overall) for each treatment group
- Difference in overall LSM changes from OP between treatment groups (rimegepant – placebo), SE, 95% CI, and p-value by randomization stratum (yes, no)
- Difference in overall LSM changes from OP between treatment groups (rimegepant – placebo), SE, 95% CI, and p-value. Results will support the second secondary objective.

These analyses will be repeated for moderate or severe migraine severity to support the first exploratory objective. All variables in the model will be the same, except (1) change from the OP in number of moderate or severe migraine days per month will be the dependent variable, and (2) number of moderate or severe migraine days per month in the OP will be the covariate.

A longitudinal plot will display the LSM change in the number of total migraine days from OP per month (y-axis) versus month of the DBT phase (x-axis). Another longitudinal plot will display the LSM change in the number of moderate or severe migraine days from OP per month (y-axis) versus month of the DBT phase (x-axis). Error bars will denote 95% CIs.

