### **Treatment Group Comparisons**

Analyses will be based on evaluable mITT subjects with MSQoL restrictive role function domain scores at both baseline and Week 12 of the on-DBT efficacy analysis period.

A generalized linear model will have the following variables: Week 12 change from baseline in the restrictive role function transformed score as the dependent variable; baseline restrictive role function transformed score as a covariate; treatment group and the prophylactic migraine medication use at randomization as fixed effects. The model will be repeated by prophylactic migraine medication use at randomization (yes, no). The following model estimates will be reported:

- LSM change from baseline at Week 12, SE, and 95% CI by randomization stratum (yes, no, overall) for each treatment group
- Difference in LSM changes from baseline between treatment groups (rimegepant – placebo) at Week 12, SE, 95% CI, and p-value by randomization stratum (yes, no)
- Difference in LSM changes from baseline between treatment groups (rimegepant – placebo) at Week 12, SE, 95% CI, and p-value. Results will support the fifth secondary objective.

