## Treatment Group Comparisons

Analyses will be based on evaluable mITT subjects with MIDAS total scores at both baseline and Week 12 of the on-DBT efficacy analysis period.

A generalized linear model will have the following variables: Week 12 change from baseline in the total score as the dependent variable; baseline total score as a covariate; treatment group and prophylactic migraine medication use at randomization as fixed effects. The model will be repeated by prophylactic migraine medication use at randomization (yes, no). The same model estimates as those described in Section 6.3.2.3 will be reported. Results will support the last secondary objective.

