## 7.4 Analysis Periods

Analysis periods are defined as follows:

- eDiary efficacy endpoints (migraine days, rescue medication days), based on the date part of derived date/times
  - OP: Reference time point date in the OP epoch (see Section 7.6.2.1).
  - On-DBT efficacy: Reference time point date in the DBT epoch on or before the DBT last date + 1 day. This period is used to assess efficacy during the DBT phase.
  - Post-DBT pre-OL rimegepant efficacy: Reference time point date in the DBT epoch after the DBT last date + 1 day. This period is used only in eDiary efficacy listings.
  - On-OL rimegepant efficacy: Reference time point date in the OLE epoch on or before the OL rimegepant last date + 1 day. This period is used to assess efficacy during the OLE phase.

- Follow-up efficacy: Reference time point date in the OLE epoch after the OL rimegepant last date + 1 day. This period is used only in eDiary efficacy listings.
  - OR efficacy endpoints (MSQoL, MIDAS)
    - On-DBT efficacy: Measurement date after the DBT start date through the earlier of (1) DBT last date + 1 day and (2) OL rimegepant start date. This period is used to assess OR efficacy during the DBT phase for evaluable mITT subjects.
  - Pre-treatment characteristics and safety endpoints
    - Pre-treatment: Measurement date/time on or before the study drug start date/time. Note that AEs with imputed start date equal to the study drug start date are **not** part of this period (refer to the BHV3000 Core SAP for AE start date imputation). This period is used to derive baseline values and to assess pre-treatment safety endpoints.
    - Pre-rimegepant: Measurement date/time on or before the DB or OL rimegepant start date/time. Note that AEs with imputed start date equal to the DB or OL rimegepant start date are **not** part of this period. This period is used to derive rimegepant baseline values and to assess pre-rimegepant safety endpoints for DB or OL rimegepant treated subjects.
    - On-DBT safety: Measurement date/time after the DBT start date/time through the earlier of DBT last date + 7 days and OL rimegepant start date/time. Note that AEs with imputed start date equal to the DBT start date are part of this period, while AEs with imputed start date equal to the OL rimegepant start date are **not** part of this period. This period is used to assess safety endpoints on DBT.

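### The rescue-medication model, third secondary in the fixed sequence, has no baseline covariate, although every other continuous endpoint in the hierarchy has one and the diary collects the data before randomisation

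*SAP*

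**What the plan says.** SAP 6.3.2.2 gives the model as "number of rescue medication days per month as the dependent variable; subject as a random effect; treatment group, prophylactic migraine medication use at randomization", plus month and the month-by-treatment interaction. That is the full list of terms. Protocol 9.5 describes the analysis as "using a generalized linear mixed effects model that is similar in structure to that used for the primary analysis".

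The neighbouring models each carry a baseline term:

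- Primary endpoint, and from the same model the overall double-blind and Month 1 migraine-day endpoints (SAP 6.3.1.1): "number of total migraine days per month in the OP as a covariate".
- MSQoL restrictive role function (SAP 6.3.2.3): "baseline restrictive role function transformed score as a covariate".
- MIDAS total score (SAP 6.3.2.4): "baseline total score as a covariate".

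On data collection, Protocol 6.3 states: "The eDiary will be used daily to record rescue medication dosing occurrences (i.e., with triptans, ergotamine, or other"; the same sentence names the Observation Period as one of the periods covered. SAP 6.3.1 says that headache status and the medication taken for it are reported "in the eDiary evening report headache log or follow-up headache log recorded every day in the OP, DBT, and OLE phases". SAP 7.4 opens its list of analysis periods, of which the OP is the first, with "eDiary efficacy endpoints (migraine days, rescue medication days), based on the date part of derived date/times". SAP 6.3.2.2 nevertheless derives rescue days only from the double-blind phase onward.

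**The concern.** Rescue medication days is the only continuous endpoint in the sequence analysed without its pre-randomisation value, and neither document says why. SAP Section 8 declares no departure from the protocol. How often a patient medicates before randomisation would ordinarily be expected to predict how often that patient medicates afterwards, so leaving it out keeps avoidable between-subject variance in the treatment contrast and leaves the estimate exposed to chance baseline imbalance.

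Position makes this matter more. Under SAP 6.1.2, a non-significant result here ends formal testing of the three endpoints behind it: Month 1 migraine days, MSQoL and MIDAS.

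**Working it through.** **1. Count of models.** The hierarchy has seven tests. One, the 50% responder rate, is binary and uses a stratified CMH test. Of the six continuous ones, five have a baseline covariate (primary, overall double-blind migraine days, Month 1 migraine days, MSQoL, MIDAS). Rescue days is the sixth and has none. The ad hoc triptan/ergotamine model in SAP 6.3.3.3 also lacks one but lies outside the hierarchy.

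**2. Availability.** Evaluable mITT status (SAP Section 3) already requires at least 14 days of eDiary efficacy data in the OP. An OP rate can therefore be formed on the diary basis already used, and no analysed subject should be lost for want of diary days.

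**3. Why the subject random effect does not do this job.** With complete data, the Month 3 contrast is the difference between two arm means. Its variance contains the full between-subject variance plus the within-subject variance. A random intercept describes how a subject's months correlate; it does not remove between-subject variance from a between-arm comparison. A baseline covariate with correlation r to the outcome, equal across months, multiplies that variance by 1 − r².

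**4. The plan's own figure.** Protocol 9.3 and SAP Section 5 assume SD 3.75, 370 evaluable per arm and a 1-day difference for the primary endpoint.

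- SE = 3.75 × √(2/370) = 0.276; 95% half-width = 1.96 × 0.276 = 0.54 days.
- Power = Φ(1/0.276 − 1.96) = 95.2%, matching the stated figure of roughly 95%.

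This is the only power statement in the documents, and it is not about rescue days.

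**5. Effect of the covariate.** The value of r is an assumption. The columns are CI width ratio √(1 − r²), equivalent sample-size multiplier 1/(1 − r²), and adjusted power for a test that has 50% or 80% power unadjusted, from Φ((1.96 + z)/√(1 − r²) − 1.96), where z is the normal quantile of the unadjusted power. None of these columns needs an SD for rescue days.

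| r | CI ratio | N multiplier | from 50% | from 80% |
|---|---|---|---|---|
| 0.3 | 0.954 | 1.10 | 54% | 84% |
| 0.4 | 0.917 | 1.19 | 57% | 86% |
| 0.5 | 0.866 | 1.33 | 62% | 90% |
| 0.6 | 0.800 | 1.56 | 69% | 94% |
| 0.7 | 0.714 | 1.96 | 78% | 98% |

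**6. In days, for illustration only.** Borrowing the migraine-day planning figures from step 4:

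| True difference | Unadjusted power | r = 0.3 | r = 0.7 |
|---|---|---|---|
| 1 day | 95% | 97% | 99.9% |
| 0.75 day | 78% | 81% | 97% |
| 0.5 day | 44% | 48% | 72% |

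The half-width falls from 0.54 to 0.52 days (r = 0.3) or 0.39 days (r = 0.7).

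**7. Simulation check.** For the Month 3 contrast with complete data, 370 per arm and 4,000 runs per value of r, the mean SE was 0.276 without the covariate and 0.263, 0.253, 0.239, 0.221 and 0.197 with it for r = 0.3 to 0.7. Type I error was 0.044–0.050 without and 0.046–0.051 with.

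**The case against.** The strongest reply is that this is a preference about efficiency. The test is valid, the protocol's wording on model structure is loose enough to permit the SAP model, and there is a visible rule: endpoints defined as a change get a baseline covariate, while the one defined as a value (Protocol 3.2, SAP 6.3.2.5) does not. All of that stands, and the point is an unexplained omission, not a contradiction. It makes the choice intelligible but does not justify it, because a value can be adjusted for its baseline as readily as a change.

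Second, the documents do not speak with one voice on OP data. Protocol 4.1, 4.3.1 and 5.5 send OP treatment to a paper diary. Footnote 8 to Protocol Table 1 mentions only whether the migraine was treated. SAP 6.3.2.2 speaks of recording in the double-blind and open-label phases, and SAP 7.6.2.2 uses triptan and ergotamine answers only in those phases. The tension is real, and the source should be named. It does not cancel the direct statements in Protocol 6.3 and SAP 6.3.1 that the eDiary captures this daily in the OP.

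Third, the size is assumed. The SD is borrowed from a change score on another endpoint, and the upper figures arise only at r = 0.7. Eligibility limits on OP migraine and headache days, and medication rules that change around baseline, could lower r. This also stands: at r = 0.3 the interval narrows by 5% and power rises by only a few points.

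Fourth, OP migraine days are already derived and could serve as the covariate. That is a reasonable fallback. The documents offer no basis for saying which would predict better; adjusting for the endpoint's own baseline is what the other five analyses do.

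**Conclusion.** The concern holds as a missed gain in precision. The rescue-day test is sound as written, but it is the one continuous test in the hierarchy that does not use pre-randomisation information the diary is said to collect. For an assumed r of 0.3 to 0.7, equal across months, the interval would be 5 to 29% narrower. The gain is small if the true effect is as large as planned for migraine days and material if it is nearer half a day. Actual power for this endpoint is unknown, so the effect on the endpoints behind it cannot be quantified. The change is worth making while it can still be prespecified.

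**What to change.** Define OP rescue medication days per month as 28 × (OP days with a positive answer for triptan, ergotamine or other headache medication) / (OP efficacy data days), which is the double-blind formula in SAP 6.3.2.2 applied to the OP. Add it as a covariate to the model there, and leave the endpoint as a value. State that the eDiary items, not the paper diary, are the source. The OP and double-blind medication lists need not match, because a covariate only has to be measured before randomisation.

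Before unblinding the cost is one derivation, one sentence and one model term. After the Week 12 unblinding it should not replace the hierarchical test. SAP version 10.0 was written after final database lock, so at that version it can only be a labelled supportive analysis. The same covariate approach could be used in the ad hoc model of SAP 6.3.3.3.
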